8.8.4.2 IIEF Erectile Function Domain Testing

End of treatment testosterone levels (<300ng/dL vs 300-500 ng/dL vs >500 ng/dL) will be tested

against IIEF erectile function domain response of achieving a minimal meaningful difference at Week 24 by a logistic regression model. The end of treatment testosterone factor effect p-value as well as the odds ratio and 95% CI of the pairwise comparison of each end of treatment testosterone level group will be presented.

This process will be repeated to test the association of baseline testosterone level (<200 ng/dL vs >200 ng/dL) against IIEF erectile function domain response of achieving a minimal meaningful difference.

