2.3 Exploratory objective(s)

The exploratory objectives are:

1. To evaluate the effect of BGS649 on oestradiol, DHT and inhibins (A and B)
2. To evaluate the effect of BGS649 on testosterone/oestradiol ratio
3. To investigate the effect on patient reported outcomes (PROs) following treatment with BGS649. PRO measures will be:
 - o International Index of Erectile Function (IIEF) and PROMIS Sexual Function and Satisfaction (PROMIS SexFS): to assess improvement in erectile function.
 - o IIEF and PROMIS SexFS: to assess improvement in sexual desire and satisfaction with sex life.
 - o 36-item Short Form Health Survey (SF-36): to assess general quality of life (QoL).
 - o Brief Fatigue Inventory (BFI), PROMIS Fatigue Short Form and the SF-36 Vitality: to assess improvement in energy levels.
 - o Patient Global Impression of Status items (PGI-S): to assess the patients' overall impression of their current health status.
4. To determine any change in physical activity and sleeping pattern via wrist worn monitor

5. To determine any change in grip strength, as measured by a dynamometer
6. To determine any associations between objective findings of improvement (e.g. testosterone, time in physical activity or sleep, and grip strength) and total and domain scores on PRO measures
7. To determine body composition change: waist circumference, BMI, body composition (as measured by impedance), and gynecomastia
8. To determine any associations between change in testosterone, body fat (as measured by BMI and waist circumference) and change in grip strength and wrist monitor data
9. To determine any associations between change in testosterone, body composition (as measured by impedance) and change in grip strength and wrist monitor data
10. To determine the effect of BGS649 on cardiometabolic parameters: systolic blood pressure (SBP) and diastolic blood pressure (DBP), lipid panel (total cholesterol, low density lipoprotein [LDL], triglycerides and HDL), glycosylated haemoglobin (HbA1c), fasting glucose and insulin, HOMA-IR and high sensitivity C reactive protein (hs CRP)
11. To determine any associations between testosterone, change in body composition and cardiometabolic parameters: SBP and DBP, lipid panel (total cholesterol, LDL, triglycerides and HDL), HbA1c, fasting glucose and insulin, HOMA-IR and hs-CRP

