7.1.3.3 International Index of Erectile Function (IIEF)

The IIEF is a 15-item self-administered questionnaire with each question being scored between 0-5 (see Appendix A for scoring conversion). Five sexual function domains will be derived by summing the scores of the associated questions (noted in parentheses below):

1. Erectile function (1,2,3,4,5,15)
2. Orgasmic Function (9,10)
3. Sexual Desire (11,12)
4. Intercourse Satisfaction (6,7,8)
5. Overall Satisfaction (13,14)

If at least one of the questions within a domain is missing then the domain will not be calculated. A higher score denotes a higher level of satisfaction/function

In addition the erectile function domain scores will be classified into the below severity categories:

- No Dysfunction (25-30)
- Mild (22-24)
- Moderate (11-21)
- Severe (1-10)

The minimal meaningful difference in the change from baseline in the erectile function domain score is defined as a change in 2 points for subjects who are mild at baseline, 5 points for subjects who are moderate at baseline and 7 points for subjects who are severe at baseline.

7.1.3.4 Patient-Reported Outcomes Measurement Information System(®) Sexual Function and Satisfaction (PROMIS(®) SexFS)

The PROMIS SexFS PRO measure will be utilized by collecting a 10 item self-administered questionnaire compiled from relevant items in the PROMIS Sexual Function and Satisfaction domains (Flynn et al., 2013). Each question is scored between 0 and 5 (See Appendix B for scoring conversion) and three sexual function domains will be derived by summing the scores of the associated questions (noted in parentheses below) and converting to a standardised T-score (standardised to a scale with mean 50 and Standard Deviation 10 – See Appendix B for conversion tables):

1. Interest in Sexual Activity (1,2)
2. Erectile Function (3)
3. Satisfaction with Sex Life (4,5,6,7,8)

If at least one of the questions within a domain is missing then the domain will not be calculated. In addition if a subject answers any question within a domain with a score of 0 (indicating the subject has not had the item in question) then the domain will also not be calculated.

Questions 9 and 10 (Interfering Factors) will be summarized by raw score as no calibration is available for interfering factors.

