8.8.4 Association Testing

To determine any correlation between endpoints at Week 24, various association testing will be conducted using the PP Population. For the below sets of endpoints scatter graphs will be generated annotated with the coefficient of determination (R^2 statistic):

- Total testosterone vs PRO scores (total and domain)
- Total oestradiol vs PRO score (total and domain)

- Testosterone/oestradiol vs PRO scores (total and domain)
- Activity parameters vs PRO scores (total and domain)
- Sleep parameters vs PRO scores (total and domain)
- Change in grip strength vs PRO scores (total and domain)
- Change in total testosterone vs Change in Grip Strength
- Change in BMI vs Change in Grip Strength
- Change in waist Circumference vs Change in Grip Strength
- Change in bio impedance parameters vs Change in Grip Strength
- Total testosterone vs cardiometabolic parameters: SBP and DBP, lipid panel (total cholesterol, LDL, triglycerides and HDL), HbA1c, fasting glucose and insulin, HOMA-IR and hs-CRP
- Change in BMI vs cardiometabolic parameters: SBP and DBP, lipid panel (total cholesterol, LDL, triglycerides and HDL), HbA1c, fasting glucose and insulin, HOMA-IR and hs-CRP
- Change in waist circumference vs cardiometabolic parameters: SBP and DBP, lipid panel (total cholesterol, LDL, triglycerides and HDL), HbA1c, fasting glucose and insulin, HOMA-IR and hs-CRP
- Change in semen parameters vs Change in LH and FSH levels
- Change in semen parameters vs Change in oestradiol
- Change in systolic blood pressure vs Total Testosterone, Oestradiol and Testosterone/Oestradiol ratio (at Week 12 and Week 24)
- Change in diastolic blood pressure vs Total Testosterone, Oestradiol and Testosterone/Oestradiol ratio (at Week 12 and Week 24)
- Change in Creatinine vs Blood Pressure (Absolute systolic and diastolic blood pressure)
- Change in Creatinine vs Change in Blood Pressure (Systolic and Diastolic blood pressure)

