8.8.4.1 PROMIS SexFS Domains Testing

End of treatment testosterone levels (<300ng/dL vs 300-500 ng/dL vs >500 ng/dL) will be tested against each PROMIS sexFS domain score (excluding the domain “interfering factors”) by a MMRM model. Analyses will include the fixed, categorical effects of end of treatment testosterone level, visit, and end of treatment testosterone level-by-visit interaction, as well as the continuous, fixed covariates of the associated baseline value and baseline-by-visit interaction. An unstructured covariance matrix will be used to model the within-subject errors. The end of treatment testosterone factor effect p-value as well as the Week 24 least square mean differences and 95% CI of the pairwise comparisons of each end of treatment testosterone level group will be presented.

This process will be repeated to test the association of baseline testosterone level (<200 ng/dL vs >200 ng/dL) against the change from baseline of each PROMIS sexFS Domain (excluding the domain “interfering factors”).

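### The only inferential test of testosterone level against the IIEF erectile function score (SAP 8.8.4.2) categorises both variables; under a roughly log-linear association it keeps about half the information

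*SAP*

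**What the plan says.** Exploratory objective 6 (SAP 2.3) asks about associations between objective findings and PRO results: "e.g. testosterone, time in physical activity or sleep, and grip strength) and total and domain scores on PRO measures". Four parts of the SAP bear on testosterone and erectile function.

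- **SAP 8.8.4.2.** Testosterone enters as a three-level factor: "End of treatment testosterone levels (<300ng/dL vs 300-500 ng/dL vs >500 ng/dL) will be tested". The outcome is binary, and the comparison is made "against IIEF erectile function domain response of achieving a minimal meaningful difference at Week 24 by a logistic regression model". A factor p-value and pairwise odds ratios with 95% CIs follow. Then: "This process will be repeated to test the association of baseline testosterone level (<200 ng/dL vs >200 ng/dL) against IIEF erectile function domain response".
- **SAP 7.1.3.3.** The responder threshold depends on baseline severity: "defined as a change in 2 points for subjects who are mild at baseline, 5 points for subjects who are moderate at baseline". For severe men it is 7 points.
- **SAP 8.8.4.1.** "End of treatment testosterone levels (<300ng/dL vs 300-500 ng/dL vs >500 ng/dL) will be tested against each PROMIS sexFS domain score" by a repeated-measures model adjusted for baseline score, with a p-value and Week 24 mean differences with 95% CIs. One of the three SexFS domains is Erectile Function, which is a single item (SAP 7.1.3.4).
- **SAP 8.8.4.** Total testosterone is set against PRO total and domain scores in the per-protocol population, where "scatter graphs will be generated annotated with the coefficient of determination". No slope, interval or test is specified.

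SAP 8.6.4.5 also analyses change in the IIEF domain scores by a repeated-measures model and repeats this within testosterone bands. Those models compare treatments with each other, not testosterone levels.

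**The concern.** The objective concerns domain scores, yet the one test that relates testosterone level to the IIEF erectile function score replaces that score with yes/no. It also replaces measured testosterone with three bands, or with two at baseline. Each cut discards information already collected. The SAP gives no reason for making both cuts here, and it handles the SexFS score differently one section earlier.

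At stake is how a negative result would be read. If 8.8.4.2 is not significant, the reader cannot tell a weak or absent association from a blunt test. The IIEF and SexFS erectile results would also come out in different units, an odds ratio and a mean difference.

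There is a drafting slip as well. The baseline bands in 8.8.4.1 and 8.8.4.2 leave out a man at exactly 200 ng/dL, whereas 8.6.4.5 uses ≥200.

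**Working it through.** **The plan's own figure.** None is given for this analysis. The only power statement (SAP 5) concerns the primary endpoint: 67 men per dose, 75% against 90%, one-sided 2.5%, power 85%. The exact binomial gives a critical value of 58/67, an attained level of 0.0160 and power of 87.1%, close to the stated figure. It has no bearing on 8.8.4.2.

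**Inputs from the documents.** Two-sided alpha 0.05 (SAP 8.1.4); three or two testosterone bands and a binary outcome (8.8.4.2); per-protocol set (8.8.4), hence at most the 268 men planned.

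**Assumed inputs.** Bivariate normal, linear association on the log-testosterone scale; 30-50% responders; bands holding one third each, or 25/25/50%; correlation r of 0.10-0.30; N of 150-268.

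**Information retained**

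1. Cutting the outcome at responder rate p keeps φ(z)²/[p(1−p)], where z is the normal quantile of p. This is 0.576 at p = 0.30 and 0.637 at p = 0.50.
2. Banding testosterone keeps the between-band share of variance. This is 0.793 for equal thirds, 0.749 for 25/25/50 and 0.637 for two equal halves.
3. Products for the three-band test run from 0.749 × 0.576 = 0.431 to 0.793 × 0.637 = 0.505. For two equal baseline bands they are 0.637 × 0.576 = 0.366 to 0.637 × 0.637 = 0.405.

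**Power where the full-scale test has 80%** (noncentrality 7.85 on 1 df)

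| Test | Power |
|---|---|
| Score uncut, testosterone in three bands | 58-60% |
| Both cut, three bands (8.8.4.2, end of treatment) | 36-41% |
| Both cut, two equal bands (8.8.4.2, baseline) | 40-43% |

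Allowing for the second degree of freedom, the three-band test needs 2.4-2.9 times the N to match the full-scale test.

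**Worked case, N = 200, r = 0.20.** Full-scale noncentrality is N·r²/(1−r²) = 200 × 0.04/0.96 = 8.33, giving power of 82%. Simulation gave about 82% full-scale against 37-41% as planned. A further simulation at the same N and r gave 82% full-scale, 63% with only testosterone banded and 39% with both cut.

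**Range, by simulation**

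| r | N | Full scale | As planned | Relative loss |
|---|---|---|---|---|
| 0.15 | 150 | 0.45 | 0.18-0.20 | 56-60% |
| 0.15 | 268 | 0.70 | 0.27-0.33 | 53-61% |
| 0.20 | 150 | 0.69 | 0.28-0.33 | 52-59% |
| 0.20 | 268 | 0.91 | 0.46-0.55 | 40-49% |
| 0.30 | 150 | 0.96 | 0.59-0.67 | 30-39% |
| 0.30 | 268 | 1.00 | 0.84-0.90 | 10-16% |

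**Step at 300 ng/dL instead of a slope.** With 20-40% of men below 300, the planned test has 67-82% power where a linear full-scale test has 80%. At N = 200, simulation of a step gave 55% for the slope, 74% for the uncut score with banded testosterone, and 44% as planned. Keeping the score continuous therefore gains power under either shape. Replacing the bands with a slope gains only if the relation is roughly linear.

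**Side effect of the responder rule.** SAP 7.1.3.3 sets no threshold for men with no dysfunction at baseline. If they were excluded, and made up an assumed 10-30% of men, retained information with equal bands would fall to 0.32-0.45. A model of the score needs no such rule.

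**The case against.** The strongest case against runs as follows. The randomised evidence on IIEF erectile function is in 8.6.4.5, on the full score scale, and is untouched by this point. SAP 8.8.4.2 compares men by achieved testosterone in the per-protocol set, which is observational. Protocol 13.5.1 calls all analyses exploratory, and no decision rests on this one. The responder outcome answers a question of its own, namely whether a man improved meaningfully for his starting severity, and fixed bands give readable contrasts. The full-scale data are also plotted: in simple regression R² and N determine the test, F = R²(N−2)/(1−R²).

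Most of this stands, and it limits the weight of the point. It does not remove it. The 8.6.4.5 models do not compare testosterone levels. The scatter plots carry no specified interval and no adjustment for baseline score. The responder question can be kept beside a model of the score.

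A reader might infer that 8.8.4.2 is the only inferential test linking testosterone to erectile function at all. The documents do not support that, because 8.8.4.1 tests the SexFS Erectile Function domain with a p-value and CIs. It is only a partial substitute: the domain is one item, and men enrolled under protocol version 2.0 were not required to complete it (8.6.4.5).

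**Conclusion.** The point holds for the IIEF erectile function score. The sole inferential test of testosterone level against it cuts both variables and keeps roughly 43-50% of the information with three bands, or 37-40% with two equal baseline bands, if the association is about linear on the log scale.

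A reader might shorten this to a flat loss of half the power. That goes too far. The relative loss is about 40-60% at correlations of 0.10-0.20 and about 10-40% at 0.30, and it is smaller for a step at 300 ng/dL, which is the trial's own lower limit of normalisation. No correlation, responder rate, band share or evaluable per-protocol number appears in the documents, so every power figure here is conditional on assumption.

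The better-supported half of the criticism is the cut of the IIEF score, which costs power under both shapes examined. The case against the bands depends on rough linearity. The analysis is exploratory and the primary endpoint is unaffected. The change is still worth making, because it is cheap and the SAP already contains the model.

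**What to change.** In SAP 8.8.4.2:

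1. Add, as the main association test, the 8.8.4.1 repeated-measures model applied to change from baseline in the IIEF erectile function domain score, adjusted for baseline score.
2. Enter log testosterone (end of treatment, and separately baseline) as a continuous covariate with its interaction by visit. Include a check for non-linearity, and report the Week 24 slope with its 95% CI.
3. Report the same model with the existing testosterone bands alongside.
4. Keep the responder logistic model as the supportive analysis of meaningful change.
5. Align the baseline cut to <200 vs ≥200 ng/dL, as in 8.6.4.5. The same wording in 8.8.4.1 needs the same correction.

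The cost is a few lines of SAP text and one extra model, with no new data: IIEF is already collected at baseline and Weeks 4, 8, 12 and 24 (Protocol Table 9–1). The small downside is that the slope assumes a roughly linear relation, which the banded results let the reader check.

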8.9 CSR

The primary efficacy analysis and study unblinding will be performed when all data up to Visit 8 (Week 24) has been collected. Given the study has been powered at Week 24 and there will not be multiple comparisons, there is no requirement to adjust the Type I error rate.

The Clinical Study report (CSR) will be prepared based upon the results of this analysis.

The data collected during the off treatment 12 week follow-up will be separately analysed and published in an addendum to the CSR.

If for any reason a primary analysis assessment (Total Testosterone) is not available at the time of the primary analysis, such values will not be used for any future efficacy endpoint analysis at any stage (i.e they will continue to be assumed missing). However such values will be included for future safety endpoints analysis (e.g Total Testosterone Overshoot).

9 CHANGES TO PLANNED ANALYSIS FROM STUDY PROTOCOL

Vitamin D deficiency is defined in the protocol as <20ng/ml. For all analyses Vitamin D deficiency has been defined as <30ng/ml.

11 APPENDICES

Appendix A - International Index of Erectile Function (IIEF)

Question Number	Question	Response	Score
1	Over the past 4 weeks how often were you able to get an erection during sexual activity?	Almost always or always	5
		Most times (much more than half the time)	4
		Sometimes (about half the time)	3
		A few times (much less than half the time)	2
		Almost never or never	1
		No sexual activity	0
2	Over the past 4 weeks when you had erections with sexual stimulation, how often were your erections hard enough for penetration?	Almost always or always	5
		Most times (much more than half the time)	4
		Sometimes (about half the time)	3
		A few times (much less than half the time)	2
		Almost never or never	1
		No sexual stimulation	0
3	Over the past 4 weeks when you attempted sexual intercourse how often were you able to penetrate (enter) your partner?	Almost always or always	5
		Most times (much more than half the time)	4
		Sometimes (about half the time)	3
		A few times (much less than half the time)	2
		Almost never or never	1
		Did not attempt intercourse	0
4	Over the past 4 weeks during sexual intercourse how often were you able to maintain your erection after you had penetrated (entered) your partner?	Almost always or always	5
		Most times (much more than half the time)	4
		Sometimes (about half the time)	3
		A few times (much less than half the time)	2
		Almost never or never	1
		Did not attempt intercourse	0
5	Over the past 4 weeks during sexual intercourse how difficult was it to maintain your erection to completion of intercourse?	Not difficult	5
		Slightly difficult	4
		Difficult	3
		Very difficult	2
		Extremely difficult	1
		Did not attempt intercourse	0
6	Over the past 4 weeks how many times have you attempted sexual intercourse?	11+ attempts	5
		7-10 attempts	4
		5-6 attempts	3
		3-4 attempts	2
		1-2 attempts	1
		No attempts	0
7	Over the past 4 weeks when you attempted sexual intercourse how often was it satisfactory for you?	Almost always or always	5
		Most times (much more than half the time)	4
		Sometimes (about half the time)	3
		A few times (much less than half the time)	2
		Almost never or never	1
		Did not attempt intercourse	0

8	Over the past 4 weeks how much have you enjoyed sexual intercourse?	Very highly enjoyable	5
		Highly enjoyable	4
		Fairly enjoyable	3
		Not very enjoyable	2
		Not enjoyable	1
		No intercourse	0
9	Over the past 4 weeks when you had sexual stimulation or intercourse how often did you ejaculate?	Almost always or always	5
		Most times (much more than half the time)	4
		Sometimes (about half the time)	3
		A few times (much less than half the time)	2
		Almost never or never	1
		No sexual stimulation or intercourse	0
10	Over the past 4 weeks when you had sexual stimulation or intercourse how often did you have the feeling of orgasm with or without ejaculation?	Almost always or always	5
		Most times (much more than half the time)	4
		Sometimes (about half the time)	3
		A few times (much less than half the time)	2
		Almost never or never	1
		No sexual stimulation or intercourse	0
11	Over the past 4 weeks how often have you felt sexual desire?	Almost always or always	5
		Most times (much more than half the time)	4
		Sometimes (about half the time)	3
		A few times (much less than half the time)	2
		Almost never or never	1
12	Over the past 4 weeks how would you rate your level of sexual desire?	Very high	5
		High	4
		Moderate	3
		Low	2
		Very low or none at all	1
13	Over the past 4 weeks how satisfied have you been with your overall sex life?	Very satisfied	5
		Moderately satisfied	4
		About equally satisfied and dissatisfied	3
		Moderately dissatisfied	2
		Very dissatisfied	1
14	Over the past 4 weeks how satisfied have you been with your sexual relationship with your partner?	Very satisfied	5
		Moderately satisfied	4
		About equally satisfied and dissatisfied	3
		Moderately dissatisfied	2
		Very dissatisfied	1
15	Over the past 4 weeks how would you rate your confidence that you could get and keep an erection?	Very high	5
		High	4
		Moderate	3
		Low	2
		Very	1

Appendix B - Patient-Reported Outcomes Measurement Information System(®) **Sexual Function and Satisfaction (PROMIS(®) SexFS)**

Question Number	Question	Response	Score
1	How interested have you been in sexual activity?	Very	5
		Quite a bit	4
		Somewhat	3
		A little bit	2
		Not at all	1
2	How often have you felt like you wanted to have sexual activity?	Always	5
		Often	4
		Sometimes	3
		Rarely	2
		Never	1
3	Please rate your ability to have an erection.	Very good	5
		Good	4
		Fair	3
		Poor	2
		Very Poor	1
4	How satisfied have you been with your sex life?	Very	5
		Quite a bit	4
		Somewhat	3
		A little bit	2
		Not at all	1
5	How much pleasure has your sex life given you?	A lot	5
		Quite a bit	4
		Somewhat	3
		A little bit	2
		None	1
6	How often have you thought that your sex life is wonderful?	Always	5
		Often	4
		Sometimes	3
		Rarely	2
		Never	1
7	How satisfied have you been with your sexual relationship(s)?	Very	5
		Quite a bit	4
		Somewhat	3
		A little bit	2
		Not at all	1
		Have not had a sexual relationship in last 30 days	0
8	When you have had sexual activity, how much have you enjoyed it?	Very much	5
		Quite a bit	4
		Somewhat	3
		A little bit	2
		Not at all	1
9	How much has fatigue or lack of energy affected your satisfaction with your sex	Very Much	5
		Quite a bit	4
		Somewhat	3

	life?	A little bit	2
		Not at all	1
		Have not had fatigue or lack of energy in the last 30 days	0
10	How much has weight gain affected your satisfaction with your sex life?	Very Much	5
		Quite a bit	4
		Somewhat	3
		A little bit	2
		Not at all	1
		Have not had weight gain in the last 30 days	0

T-Score Conversion Tables :

1. Interest in Sexual Activity (1,2)

Q1 Raw	Q2 Raw	T Score
1	1	33.4
1	2	40.1
1	3	44.5
1	4	50.3
1	5	55.3
2	1	39.8
2	2	43.6
2	3	47.6
2	4	52.7
2	5	57.4
3	1	43.1
3	2	46.7
3	3	51.1
3	4	55.5
3	5	60.1
4	1	45.4
4	2	49.3
4	3	54.5
4	4	59
4	5	63.8
5	1	47.1
5	2	51.2
5	3	57.5
5	4	63.2
5	5	70

2. Erectile Function (3)

Q3 Raw	T score
1	31.4
2	36.6
3	40.4
4	45.6
5	56.3

3. Satisfaction with Sex Life (4,5,6,7,8)

Satisfaction with Sex
Life Tscore.xlsx

